#### Handling of Missing Data

Initial descriptive statistics will be performed to quantify univariate missingness and distribution of variables. Observed values that appear to be extreme will be verified with the research staff for accuracy. If extreme values do not appear to exhibit undue influence on the statistical methods they will be kept in the analysis. Otherwise they will be removed. Extreme values found to be erroneous will be corrected.

Missing values for outcomes (e.g. VAS, opioid consumption, etc) will be imputed using the last observation carried forward method. Since we expect downward trends in these observations as time from procedure increases, this method will provide a conservative between-treatment estimate of the effect (assuming the observations are missing at random and are roughly missing with equal frequency within each treatment group).

These results will be compared to the results of a linear mixed-model which doesn't require that every patient has data for every measure at every point in time. Instead, it all information recorded and only excludes those time points at which data is missing. For example, if a patient is missing data at 48 hours, then the linear mixed-model will only include the data at 24 hours and 72 hours. In contrast, the last observation carried forward method would use the observed value from 24 hours for the 48 hour value and then all three time points will be included. In both cases, the baseline values for VAS and opioid consumption must be known for the patient to be included in the analysis.

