#### Multiplicity

There is only one primary hypothesis so we will not adjust for multiplicity at the highest level. However, if the linear mixed-model shows that the time by treatment interaction term is statistically significant and we perform post-hoc pairwise comparisons, the Tukey-Kramer

method will be used to adjust for multiple comparisons. There are several secondary aims that we consider exploratory analyses and as such will not adjust for multiple comparisons.

**Primary Hypothesis:** The average post-op pain score, adjusted for baseline pain scores, over the 72 hours post-op will be significantly lower in the liposomal bupivacaine group.

The difference in post-operative numeric pain scores between the treatment groups over time will be analyzed using a linear mixed-model with an interaction term for time and treatment and will adjust for the baseline (pre-op) scores.

**Secondary Hypothesis 1:** The average post-op satisfaction score over the 72 hours post-op will be significantly lower in the liposomal bupivacaine group.

The difference in post-operative numeric satisfaction scores between the treatment groups over time will be analyzed using a linear mixed-model with an interaction term for time and treatment.

**Secondary Hypothesis 2:** Time to block cessation will be longer in the liposomal bupivacaine group than the standard bupivacaine group.

The difference in time to block cessation will be analyzed between treatment groups using a two sample t-test if necessary model assumptions are met or the Wilcoxon Rank-Sum test if assumptions are not met.

**Secondary Hypothesis 3:** Total opioid consumption will be significantly lower in the liposomal bupivacaine group.

The distribution of total opioid consumption for the two groups will be compared using a multiple linear regression model with a term to adjust for baseline opioid consumption.

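### LOCF is called conservative because outcomes fall over time, but its bias follows the between-arm gap, not the trend, and the plan does not say whether LOCF or the mixed model governs

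*Combined protocol and SAP*

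**What the plan says.** Under Handling of Missing Data in Section 7.2, LOCF is the stated rule: "Missing values for outcomes (e.g. VAS, opioid consumption, etc) will be imputed using the last observation carried forward method". The justification is "Since we expect downward trends in these observations as time from procedure increases, this method will provide a conservative between-treatment estimate", on condition that data are missing at random and about equally often in the two arms. The worked example has scores at 24, 48 and 72 h with the 48-h score missing; LOCF "would use the observed value from 24 hours for the 48 hour value".

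On the relation to the other method the section says "These results will be compared to the results of a linear mixed-model", a model that "only excludes those time points at which data is missing". It adds "In both cases, the baseline values for VAS and opioid consumption must be known" for a patient to be analysed.

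For the primary hypothesis (printed under Multiplicity in Section 7.2), pain over 72 h "will be analyzed using a linear mixed-model with an interaction term for time and treatment and will adjust for the baseline (pre-op) scores". That text does not mention LOCF and does not say which data set the model is fitted to. Total opioid consumption (Secondary Hypothesis 3) is analysed by a linear regression on one total per patient.

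**The concern.** A trend shared by both arms concerns the level of pain. The treatment effect is a difference, and LOCF biases a difference only through changes in that difference over time. The two conditions the plan attaches say nothing about how the gap evolves.

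The plan's own text makes a changing gap likely. Section 1.1 gives a standard block 12 to 24 h. Section 6.2 scores the end of a block as pain reaching 3 or more. Secondary Hypothesis 2 states "Time to block cessation will be longer in the liposomal bupivacaine group than the standard bupivacaine group". Taken together, these imply that pain rises when a block ends, and at different times in the two arms. A 24-h score carried to 48 h starts close to the end of a standard block.

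Two things are at stake. Readers would rely on a protective property that does not hold in general. And because the LOCF and mixed-model results are not ranked, the choice between them could be made after both have been seen.

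**Working it through.** The plan gives no figure for the size or direction of LOCF bias, so there is none to reproduce. The check is whether the stated property follows from the stated conditions.

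**Inputs from the plan.** Equal missingness by arm (Section 7.2); standard block 12 to 24 h (Section 1.1); pain scores every 4 h in hospital (Section 6.2), then twice daily to 72 h (Section 6.3); planning difference 2 points (Section 7.1).

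**Assumed, because the plan does not give them.** Pain curves, discharge time, liposomal block duration and non-response rate.

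**1. Direction of the bias.** Let D(t) be the true gap (control minus liposomal) at time t. Suppose a fraction q of each arm, unrelated to pain, has no score after time s. For t > s:

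- expected LOCF gap = (1 - q) x D(t) + q x D(s)
- bias = q x [D(s) - D(t)]

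The pain level in either arm does not enter; only the change in the gap does.

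**2. Both arms declining, q = 0.20, s = 24 h.** LOCF average = 0.8 x true average + 0.2 x 24-h gap.

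| Control 24/48/72 h | Liposomal 24/48/72 h | Gap | True average | LOCF average |
|---|---|---|---|---|
| 6, 5, 4 | 4, 3.5, 3 | 2, 1.5, 1 | 1.50 | 0.8 x 1.5 + 0.2 x 2 = 1.60 |
| 5, 4.5, 4 | 4, 3, 2 | 1, 1.5, 2 | 1.50 | 0.8 x 1.5 + 0.2 x 1 = 1.40 |
| 6, 5, 4 | 4.5, 3.5, 2.5 | 1.5 throughout | 1.50 | 1.50 |

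All three rows meet the plan's downward-trend and equal-missingness conditions, and the first overstates the effect. A separate simulation used a true average gap of 2.00, with 10% of those remaining lost before 48 h and again before 72 h. It gave LOCF averages of about 2.13 (narrowing), 2.00 (parallel) and 1.87 (widening) when missingness depended on the last observed score, and the same pattern when it was completely random.

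**3. The plan's 24-to-48-h example.** Assumed curves: pain 1 while blocked, rising over 6 h to 5 (control) or 4 (liposomal), then falling 0.04 per hour; liposomal block ends at 36 h.

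- Control block ends at 16 h. At 24 h: (5 - 0.04 x 2) - 1 = 3.92. At 48 h: (5 - 0.04 x 26) - (4 - 0.04 x 6) = 3.96 - 3.76 = 0.20. LOCF carries 3.92 in place of 0.20.
- Control block ends at 24 h. At 24 h both arms are at 1, gap 0.00. At 48 h: 4.28 - 3.76 = 0.52. LOCF carries 0.00 in place of 0.52.

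**4. Shift in the 72-h mean.** Same curves; scores every 4 h to discharge, then those of 36, 48, 60 and 72 h that fall later, equally weighted. A fraction q misses all post-discharge scores. With discharge at 24 h and q = 0.20:

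- Control end 16 h: true 10.627/10 = 1.063; with the 24-h gap carried throughout, 22.267/10 = 2.227; LOCF = 0.8 x 1.063 + 0.2 x 2.227 = 1.295, a shift of +0.23.
- Control end 24 h: true 5.32/10 = 0.532; carried mean 0; LOCF = 0.8 x 0.532 = 0.426, a shift of -0.11.

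Over control ends of 12 to 24 h and q of 10% to 20%:

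| Liposomal block end | Discharge | Shift |
|---|---|---|
| 36 h | 24 h | -0.11 to +0.23 |
| 36 h | 28 h | +0.05 to +0.20 |
| 36 h | 32 h | +0.09 to +0.17 |
| 36 h | 36 h | +0.08 to +0.16 |
| 36 h | 48 h | 0 |
| 48 or 60 h | 24 h | -0.19 to +0.20 |
| 48 or 60 h | 48 h | +0.03 to +0.09 |
| 72 h | 24 h | -0.24 to +0.10 |

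If each post-discharge survey is missed independently (discharge 24 h, liposomal end 36, 48 or 60 h), the shift is -0.01 to +0.10. If both arms share one curve, D(t) = 0 throughout and the expected shift is zero, so no type I error inflation is claimed.

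**5. Observed-data mixed model.** Simulated on the curves of step 4 with the time-by-treatment, baseline-adjusted model (random intercept, REML; 1,500 trials per scenario, 50 per arm, SD 3, correlation 0.5, Monte Carlo SE 0.009). At 10%/20% random missingness the model gave 1.056/1.058 against a truth of 1.063, and 0.517/0.531 against 0.532. LOCF gave 1.172/1.287 and 0.464/0.419. Missingness depending on the last in-hospital score gave the same picture.

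**6. 72-h opioid total.** Assumed daily amounts, days 2 and 3 missing and day 1 carried.

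- 30/25/15 versus 10/20/15: true difference 70 - 45 = 25; carried 90 - 30 = 60. At 10%, 0.9 x 25 + 0.1 x 60 = 28.5; at 20%, 32.
- 10/30/20 versus 8/15/20: true difference 60 - 43 = 17; carried 30 - 24 = 6. At 10%, 15.9; at 20%, 14.8.

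**The case against.** **The ranking can be inferred.** The primary hypothesis has one analysis, a mixed model; the missing-data section describes such a model as using observed time points and contrasts LOCF with it. That is the likeliest reading. But LOCF is stated first, as the rule, and no sentence names the data set for the primary model or the governing result. What stands is that one sentence would settle it.

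**The sizes rest on assumed curves, and 12% is not a bound.** This is correct. Time-weighting the curves of step 4 (discharge at 24 h, 20% missing) gives shifts up to about 0.4 points. In the other direction, isolated missed surveys do little, and Section 6.5 has the coordinator chase non-responders. The logical fault in step 1 does not depend on any of these curves.

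**The direction rule is clean only when the gap moves one way.** This also stands. If the gap opens and then closes, the sign depends on when data are lost, which is a further reason not to promise a direction.

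**The mixed-model check is favourable by design.** The fitted covariance matches the simulated one, missingness is random or depends on an observed score, and the plan specifies neither a random intercept nor REML. The check shows that the remedy works under the plan's own missing-at-random assumption, and no more.

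**The opioid strand is over-read.** The baseline requirement may be only an inclusion condition, not a promise of a mixed model for opioids. Even so, LOCF remains the only handling that clearly applies to a regression on one total. Secondary aims are declared exploratory, so little hangs on it.

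**Conclusion.** The concern holds. The claim that LOCF is conservative is wrong under the plan's own conditions; this is an error of reasoning, not a missing detail. The likely effect on the primary result is small: under the equally weighted assumed curves the largest shifts are +0.23 and -0.24, and 0.24/2 = 12% of the planning difference. The real size depends on discharge time, block duration and non-response, none of which the documents give. The absence of a stated ranking between LOCF and the mixed model is a second, smaller gap. Overall the point is minor. The opioid point is subsidiary, and the conclusion does not depend on it.

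**What to change.** In Section 7.2:

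1. Delete the sentence that calls LOCF conservative.
2. State that the baseline-adjusted linear mixed model of the primary hypothesis, fitted to all observed pain scores without imputation, is the single primary analysis and governs if results differ.
3. Keep LOCF, if at all, as a labelled sensitivity analysis.
4. For the 72-h opioid total only, multiply impute missing daily amounts before summing, in place of LOCF. This does not apply to the 3-week total, which Section 6.4 takes from a pill count.

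The cost is SAP wording and a little programming. No new data are needed and the sample size does not change.

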#### Multiplicity

There is only one primary hypothesis so we will not adjust for multiplicity at the highest level. However, if the linear mixed-model shows that the time by treatment interaction term is statistically significant and we perform post-hoc pairwise comparisons, the Tukey-Kramer

method will be used to adjust for multiple comparisons. There are several secondary aims that we consider exploratory analyses and as such will not adjust for multiple comparisons.

**Primary Hypothesis:** The average post-op pain score, adjusted for baseline pain scores, over the 72 hours post-op will be significantly lower in the liposomal bupivacaine group.

The difference in post-operative numeric pain scores between the treatment groups over time will be analyzed using a linear mixed-model with an interaction term for time and treatment and will adjust for the baseline (pre-op) scores.

**Secondary Hypothesis 1:** The average post-op satisfaction score over the 72 hours post-op will be significantly lower in the liposomal bupivacaine group.

The difference in post-operative numeric satisfaction scores between the treatment groups over time will be analyzed using a linear mixed-model with an interaction term for time and treatment.

**Secondary Hypothesis 2:** Time to block cessation will be longer in the liposomal bupivacaine group than the standard bupivacaine group.

The difference in time to block cessation will be analyzed between treatment groups using a two sample t-test if necessary model assumptions are met or the Wilcoxon Rank-Sum test if assumptions are not met.

**Secondary Hypothesis 3:** Total opioid consumption will be significantly lower in the liposomal bupivacaine group.

The distribution of total opioid consumption for the two groups will be compared using a multiple linear regression model with a term to adjust for baseline opioid consumption.

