### **5.3 Method for Assigning Subjects to Treatment Groups**

Our 110 participants will be equally randomized to one of two treatment arms using a randomized block strategy with varying block sizes. The randomization list will be created in SAS v9.4 (SAS Institute; Cary, NC) and will be uploaded into the REDCap randomization module.

The pharmacy team, the study coordinator, and the statistician will have access to the randomization module with the pharmacy team serving as the primary randomizers and the study coordinator and statistician serving as back-ups. Only the statistician will have knowledge of how the randomization list was built and will be the only one that has seen it.

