## 7 Statistical Plan

### 7.1 Sample Size Determination

Using an equal-variance t-test with a multiplicity-adjusted alpha of 0.0167 (0.05/3), we need 55 subjects per group in order to achieve 80% power to detect a true effect size of 0.66 or larger. The total sample size of 110 includes 10 additional patients to protect against an estimated attrition rate of 10%. The effect size was estimated using an established MCID of 2 for VAS pain scales and a standard deviation of 3.

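### Tukey-Kramer, with no stated family, fits the between-arm comparisons over time poorly: conservative across all cells, no adjustment within a time point

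*Combined protocol and SAP*

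**What the plan says.** The statistical plan (section 7.2, Multiplicity) states: "if the linear mixed-model shows that the time by treatment interaction term is statistically significant and we perform post-hoc pairwise comparisons, the Tukey-Kramer" and continues "method will be used to adjust for multiple comparisons". It does not say whether the pairs are all arm-by-time cells or the two arms within each time.

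The comparisons are conditional on the interaction and sit below the primary hypothesis. That hypothesis concerns one quantity: "The average post-op pain score, adjusted for baseline pain scores, over the 72 hours post-op will be significantly lower" in the liposomal group. For it the plan says: "There is only one primary hypothesis so we will not adjust for multiplicity at the highest level".

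Subjects are "equally randomized to one of two treatment arms" (section 5.3). The times entering the mixed model are not fixed. The missing-data text in section 7.2 uses 24, 48 and 72 hours as an example. Section 6.2 records pain every 4 hours in hospital, and section 6.3 twice daily after discharge up to 72 hours.

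Section 7.1 sizes the trial at an alpha of 0.05/3 "in order to achieve 80% power to detect a true effect size of 0.66 or larger", without saying which three comparisons the divisor refers to.

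**The concern.** When the treatment effect varies over time, the next question is when the arms differ. With two arms that is one contrast per time point. Tukey-Kramer is built for all pairwise differences among a set of means, which is a different family.

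If the set is every arm-by-time cell, most of the correction goes on pairs such as 24 against 72 hours in the same arm. If the set is the two arms at one time, there is a single pair and nothing to correct, so multiplicity across times is left to the interaction test alone.

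At stake are the statements about when the longer-acting block helps. The wording also lets the analyst choose between a strict and an absent adjustment after seeing the data.

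**Working it through.** **Inputs.** Two arms, 1:1 (section 5.3). 50 analysable per arm (section 3.2). Effect size d = 0.66, from a difference of 2 and an SD of 3 (section 7.1). Assumptions not in the plan: 3 times (borrowed from the 24/48/72-hour example), with 10 times as a denser case; equal SD at each time; equal correlation of 0, 0.5 or 0.7 between times; 98 degrees of freedom.

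**1. The plan's own figure.** Noncentrality is d·√(n/2) = 0.66 × √25 = 3.30. With two-sided alpha 0.05/3 and 98 df the critical t is 2.436, and power is 80.4%. So 50 per arm reproduces the planned 80%. With 55 per arm, the number section 7.1 calls needed, power is about 85%; 55 is the enrolled figure.

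**2. Tukey-Kramer over all cells.** Three times give 2 × 3 = 6 cells and 6 × 5/2 = 15 pairs. Three are same-time arm contrasts, six are within-arm and six are cross-arm at different times. The critical value is the 95% studentized range quantile divided by √2: 4.111/1.414 = 2.907, a per-pair alpha of 0.0045. Bonferroni on the 3 contrasts uses 2.436. Power at noncentrality 3.30:

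- 3 times: 65% (Tukey-Kramer) against 80% (Bonferroni).
- 10 times (20 cells, 190 pairs, 10 of interest): 37% against 67%.

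Under no arm difference, the realised error of the all-cell version over the 3 arm contrasts is 1.0% to 1.3% before the interaction condition. It is valid but spends little of its 5%.

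**3. Tukey-Kramer within a time point.** With two means the critical value is 2.806/1.414 = 1.984, which is exactly the unadjusted t at 98 df.

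**4. Adding the interaction condition.** Comparisons are made only if the interaction is significant. I simulated arm contrasts as correlated normal statistics, tested equality of the arm difference across times (chi-square, number of times minus 1 df, 5% level), and counted rejections only when that test was passed. For the within-time reading:

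| Times | Correlation | False positive, no arm difference at any time | False positive elsewhere, one time truly differs by 0.66 |
|---|---|---|---|
| 3 | 0 | 4.3% | 7.4% |
| 3 | 0.5 | 2.4% | 8.5% |
| 3 | 0.7 | 1.6% | 8.3% |
| 10 | 0 | 4.9% | 27% |
| 10 | 0.5 | 3.5% | 25% |
| 10 | 0.7 | 2.3% | 20% |

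Power to detect the one true difference among 3 times, after the condition, at correlations 0, 0.5 and 0.7: all-cell Tukey-Kramer 58%, 66% and 67%; Bonferroni 64%, 79% and 82%. These use large-sample critical values (2.850 and 2.394). Without the condition the same values give 67% and 82%, slightly above the t-based 65% and 80% in step 2.

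**5. The matched family.** Bonferroni on 3 contrasts, after the condition and with one true difference, gives a false-positive chance of 2.6% to 3.0%. Holm rejects everything Bonferroni rejects, so it has at least that power, and it keeps familywise error at or below 5%.

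**The case against.** Tukey-Kramer is a standard method for pairwise comparisons, which is what the plan says it will make. A reader might infer that it is the wrong method or gives invalid results. The documents do not support that: over all cells it controls familywise error, and the cost is efficiency. Calling the other pairs irrelevant also presumes a family the plan has not defined. The two-arm design and the stated interest in the difference between groups over time make that family likely, not certain.

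A reader might also quote the unadjusted false-positive rates for the within-time reading: 11% to 14% over 3 times, or 21% to 40% over 10, at correlations of 0.7 to 0. Those rates omit the interaction condition. With it, error stays at or below 5% when the arms never differ. What survives is the case where one time truly differs: the interaction test is then likely to be passed and no longer protects the other times.

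The power gap depends on the pattern of effects as well. With 3 uncorrelated times it narrows to 58% against 64%. If the arms differ equally at every time, the interaction test is passed only about 5% of the time and the choice of adjustment hardly matters.

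Finally, one might read 0.05/3 in section 7.1 as three time-point tests and conclude that the trial falls short of its planned power. The plan never says what the three comparisons are, so that remains conjecture.

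**Conclusion.** The point holds as a mismatch between method and likely family, made worse because the family and the time points are not stated. On one reading the follow-up contrasts lose up to about 15 percentage points of power with 3 times. On the other, they carry a false-positive chance above 5% when one time truly differs: modestly above with 3 times, well above with an assumed 10. The sizes rest on the assumed number of times, the correlation, equal SDs and 50 per arm.

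The importance is low. The comparisons are post-hoc and conditional, and the primary test of the 72-hour average does not depend on them.

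**What to change.** In section 7.2, name the post-operative time bins that enter the mixed model. Define the post-hoc family as the between-arm contrast at each bin. Replace Tukey-Kramer with a simulation-based (multivariate-t) or Holm adjustment over those contrasts. Say in section 7.1 what the divisor 3 refers to, so that the two sections agree.

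This needs a few sentences and a different software option, with no extra data or patients. The costs are small but real. The bins must be fixed in advance and reconciled with 4-hourly and then twice-daily recording. Within-arm and cross-time pairs lose adjusted inference. Holm does not give simple simultaneous confidence intervals; if intervals are wanted, the simulation-based version is the better choice.

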### 1.1 Background

The “Opioid Crisis” has been characterized by a significant rise in the prevalence of opioid dependence and drug related deaths. Not only has this placed a substantial strain on the health care economy, but resultant government legislation has led to greater restrictions on narcotic prescriptions. Consequently, there has been increasing interest in the development of multi-modal pain control regimens, particularly, in the post-operative period.

Furthermore, in those patients undergoing orthopedic surgery, adequate pain control is highly important. Patients with poor post-operative pain management in the first 48 hours have an approximate 50 percent chance of achieving long-term satisfactory pain relief. Inadequate pain management has been shown to not only increase hospital length of stay, but increase the risk of thromboembolic events, pulmonary complications, and chronic pain. Regional analgesia through the use of local anesthetic agents is a commonly employed strategy for pain management. In shoulder surgery, specifically, peripheral nerve block with long acting local anesthetic is a well-established technique for pain control. Typical agents including bupivacaine and ropivacaine, in general, provide a block duration of 12 to 24 hours.

In 2011, liposomal bupivacaine (Exparel, Pacira Pharmaceuticals, San Diego, USA) was approved by the US Food and Drug Administration (FDA) for use as a local anesthetic for surgical site infiltration. Liposomal bupivacaine is composed of a phospholipid bilayer that encapsulates bupivacaine, extending drug delivery for up to 72 hours and potentially extending periods of regional analgesia. Early studies evaluating liposomal bupivacaine noted lower subjective pain scores, increased time to first opiate medication, and decreased opiate requirements when compared to placebo.

Liposomal bupivacaine was FDA-approved for use in interscalene nerve blocks (INB) in the setting of shoulder surgery on April 6, 2018. Despite approval, there is limited data comparing liposomal bupivacaine to traditional agents in this population. The objective of this study is to determine if peripheral nerve block with liposomal bupivacaine in combination with standard bupivacaine will prolong the duration of block, improve pain scores, and decrease opioid utilization in the post-operative period when compared to peripheral nerve block with standard bupivacaine alone.

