## 2 Study Objectives

The primary outcome measure will be:

1. Mean difference in patient pain scores over the first 72 hours post-operatively between two groups

Secondary outcomes will include:

1. Total opioid consumption (as measured utilizing morphine intravenous equivalents) in first 72 hours and at 3 weeks
2. Patient perceived duration of block determined as the time patient perceives complete resolution of block
3. Patient satisfaction with pain control at 72 hours, 3 weeks post-operatively and patient reported outcome measures (SANE, SST, ASES, VR-12) at 3 weeks post-operatively

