## **6.2 Surgical Stay**

Patient reported pain will be measured utilizing visual analogue scales – VAS at 4 hour intervals during the duration of their inpatient hospitalization following surgery. Further, time until cessation of the nerve blockade as quantified as time to patient reported cessation of the nerve blockade, and time until first opioid rescue will be noted. Patients and nursing staff will be educated on how to accurately quantify time to patient reported cessation of the nerve blockade as follows: pain scores of 3 or greater at surgical site will be considered as time of cessation of nerve block.

Furthermore, all narcotic utilization during the hospitalization will be recorded. All values will be presented as morphine equivalents.

Operative time, laterality of surgery, length of stay, and disposition at discharge from the hospital will additionally be collected.

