### 6.3 Time from discharge to first post-operative visit

At discharge, pain scores will be measured utilizing electronically managed surveys that will be e-mailed to each patient on a twice daily basis (upon waking the AM and just prior to bedtime) after discharge for the first 72 hours following surgery. Finally, patient satisfaction scores (Likert scores) will be emailed to the subjects at 72 hours.

Total opioid consumption will similarly be measured based off of electronically managed surveys or a written diary on a daily basis following discharge for the first 72 hours. All values will be presented as morphine equivalents.

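### Block duration is defined in two ways, is not assigned for collection after discharge, and has no rule for unresolved blocks, so the planned comparison can understate the difference between arms

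*Combined protocol and SAP*

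**What the plan says.** Section 2 lists the secondary outcome as "Patient perceived duration of block determined as the time patient perceives complete resolution of block". Section 6.2, Surgical Stay, starts from patient-reported cessation but then instructs patients and nurses that "pain scores of 3 or greater at surgical site will be considered as time of cessation of nerve block".

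The time of cessation is called for only in Section 6.2. After discharge, Section 6.3 collects pain scores "on a twice daily basis (upon waking the AM and just prior to bedtime) after discharge for the first 72 hours", plus opioid use and satisfaction. Neither Section 6.3, the 3-week visit in Section 6.4, nor the Schedule of Events has an item for block cessation.

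Section 7.2 gives the analysis: "time to block cessation will be analyzed between treatment groups using a two sample t-test if necessary model assumptions are met", otherwise the Wilcoxon rank-sum test. Censoring is not mentioned. The general missing-data rule is "Missing values for outcomes (e.g. VAS, opioid consumption, etc) will be imputed using the last observation carried forward method". On status, Section 7.2 says "There are several secondary aims that we consider exploratory analyses", without adjustment for multiple comparisons.

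Section 1.1 makes prolonging the block part of the study objective. It says standard agents "provide a block duration of 12 to 24 hours" and describes the liposomal product as "extending drug delivery for up to 72 hours".

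**The concern.** Return of sensation and return of pain are different events. A patient whose block wears off without pain ever reaching 3 has an event under Section 2 and none under Section 6.2. Section 7.2 does not say which time is tested.

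The second problem is follow-up. A block still working at discharge has no observed end under the stated collection. If the hypothesis is true, this happens more often in the liposomal arm, so the missing times are the long ones the comparison is meant to detect. The analyst would have to decide after the fact whether to drop those patients, enter discharge time, or rank them last, and these choices give different answers. The rule in Section 7.2 that lets influential extreme values be removed could also take out genuine long blocks.

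**Working it through.** **Does the missing-data rule close the gap?** No. Last observation carried forward is illustrated with repeated measures at 24, 48 and 72 h. A time to event is one value per patient, with no earlier value to carry. Its justification also assumes roughly equal missingness in the two arms, which would fail here if the hypothesis is true.

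**Inputs.** The plan gives no effect, SD or power for block duration, so it has no figure of its own to reproduce for this outcome. I took 50 evaluable patients per arm from Section 3.2. That number does reproduce for the primary endpoint: effect size 0.66, two-sided alpha 0.0167 and an exact t-test give 50 per group, power 80.5%. The rest are assumptions: lognormal times, control median 18 h (middle of 12–24 h), liposomal median 36 h, log-SD s = 0.4, and a common observation cutoff c.

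**Formulas.** For median m and z = ln(c/m)/s:

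- true mean = m·exp(s²/2)
- share unresolved = 1 − Φ(z)
- mean with unresolved times set to c = m·exp(s²/2)·Φ(z − s) + c·[1 − Φ(z)]
- mean with unresolved patients dropped = m·exp(s²/2)·Φ(z − s)/Φ(z)

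**True difference.** 36·exp(0.08) − 18·exp(0.08) = 39.0 − 19.5 = 19.5 h.

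**Worked case, c = 24 h.**

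- Control: z = ln(24/18)/0.4 = 0.719; unresolved 0.236. Set: 19.50 × 0.625 + 24 × 0.236 = 17.86 h. Dropped: 12.19/0.764 = 15.96 h.
- Liposomal: z = ln(24/36)/0.4 = −1.014; unresolved 0.845. Set: 39.00 × 0.0786 + 24 × 0.845 = 23.34 h. Dropped: 3.07/0.155 = 19.76 h.
- Difference: 5.5 h set, 3.8 h dropped.

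| Cutoff | Unresolved, control / liposomal | Set to cutoff | Dropped |
|---|---|---|---|
| 24 h | 24% / 84% | 5.5 h | 3.8 h |
| 36 h | 4% / 50% | 12.2 h | 8.4 h |
| 48 h | 1% / 24% | 16.3 h | 12.7 h |
| 72 h | 0% / 4% | 18.9 h | 17.5 h |

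**Mixed discharge.** With half the patients discharged at 24 h and half at 48 h, 12% and 54% are unresolved. The estimate is 10.9 h with discharge time used and 12.0 h with patients dropped.

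**Range.** Over liposomal medians 30, 36 and 48 h and log-SD 0.3, 0.4 and 0.6, the share of the true difference kept is:

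| Cutoff | Set to cutoff | Dropped |
|---|---|---|
| 24 h | 17–41% | 11–28% |
| 48 h | 53–97% | 34–88% |
| 72 h | 75–99.9% | 55–99% |

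**A different distribution.** With control times uniform on 12–24 h and liposomal times lognormal with mean 24 h and coefficient of variation 0.4, a 24 h cutoff leaves 43% of liposomal blocks unresolved and no control blocks. The true difference of +6.1 h becomes +2.4 h (set) or −0.3 h (dropped).

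**Power of the test.** Simulated with 50 per arm, two-sided 0.05, log-SD 0.4 and a 24 h cutoff. At medians 18 and 24 h, Wilcoxon has 93% with full data, 91% with unresolved patients tied last and 40% if they are dropped; log-rank has 89%. At medians 18 and 36 h, Wilcoxon is close to 100% with full data or tied last, and 62% if patients are dropped.

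**The case against.** The strongest reply is that Section 7.2 uses the word cessation, as Section 6.2 does, and Section 6.2 gives an operational rule based on pain. On that reading the data exist: pain every 4 hours in hospital, then twice daily to 72 h, with coordinator follow-up of missed surveys. The inclusion criteria also mention a written diary of events. The 72 h row would then apply, keeping 97% (set) or 90% (dropped) of the difference in the central case.

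This stands in part. The home scores could give a coarse, interval-censored time to pain of 3. But the plan does not say they will be used for this outcome, and they cannot show perceived resolution, which is the definition in Section 2.

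A second reply is that the tests are not at fault: Wilcoxon loses almost nothing if unresolved patients are ranked last, and it slightly outperforms log-rank. That is correct. The damage comes from dropping patients or treating discharge as the event, and the plan neither prescribes nor excludes either.

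Third, the medians, spread and discharge times are assumed, and the 72 h figure in Section 1.1 concerns drug delivery, not block duration. This is also correct, and is why the size is given as a range. The conflict between definitions has no fixed direction; the understatement follows from the unresolved blocks alone.

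**Conclusion.** The concern holds and should be fixed. The two definitions conflict, collection of the event after discharge is not assigned, and no rule covers unresolved blocks.

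The size depends mainly on how long patients are observed. In the central case the estimate keeps 28% (5.5/19.5) or 19% (3.8/19.5) of the true difference at a 24 h cutoff, and 97% or 90% at 72 h. These figures rest on assumed lognormal times and an unstated length of stay. The bias runs mainly toward no effect. Because the outcome is secondary and exploratory, the trial's main conclusion on pain does not depend on it.

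**What to change.** 1. Reconcile Sections 2 and 6.2 to one prespecified definition for Secondary Hypothesis 2, and report the other separately.
2. Add one question to the twice-daily survey or diary already running to 72 h: has the block fully worn off, and if so when?
3. State that a block unresolved at last contact or 72 h is censored there. Patients are not dropped, and discharge time is not used as the event.
4. Estimate by Kaplan-Meier, with medians or the restricted mean to 72 h, and test by log-rank or an interval-censored equivalent. If Wilcoxon is kept, follow everyone to the same 72 h limit and rank unresolved patients last.

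The cost is one survey item and a few lines of SAP text. A median or restricted mean replaces a simple mean, and log-rank may have slightly less power than Wilcoxon (89% against 91% in the case above). Censoring at last contact assumes that loss of contact is unrelated to block duration, so incomplete follow-up should be reported by arm. The gain is a sounder estimate and a rule fixed in advance, not more power.
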